10.1.7 Serious Adverse Event (SAE)/ Serious Suspected Adverse Reaction

An SAE is defined as any untoward medical occurrence that at any dose:

- 1. Results in death.
- 2. Is life threatening.
 - The term "life threatening" refers to an event in which the subject was at risk of death at the time of the event; it does not refer to an event that hypothetically might have caused death if it were more severe.
- 3. Requires inpatient hospitalization or prolongation of existing hospitalization.
- 4. Results in persistent or significant disability/incapacity.
- 5. Leads to a congenital anomaly/birth defect.
- 6. Is an important medical event that satisfies any of the following:
 - May require intervention to prevent items 1 through 5 above.
 - May expose the subject to danger, even though the event is not immediately life threatening or fatal or does not result in hospitalization.

10.1.8 Life-Threatening Adverse Event/Life-Threatening Suspected Adverse Reaction

A life-threatening AE/life-threatening suspected adverse reaction, in the view of either the Investigator or Sponsor, places the patient or suspect at immediate risk of death. It does not include an adverse reaction that, had it occurred in a more severe form, might have caused death.

The determination of whether an AE is life threatening can be based on the opinion of the Investigator or Sponsor. If either, the Sponsor or investigator believes that the event is serious or life threatening, the event must be considered serious and evaluated by the Sponsor for expedited reporting (21 CFR 312.32(a) and 312.32(c)(1)).

10.2 Severity of AEs

The different categories of intensity (severity) are characterized as follows:

Mild: The event is transient, easily tolerated by the subject and does not

affect the subject's daily activities.

Moderate: The event causes the subject discomfort and interrupts the subject's

usual daily activities.

Severe: The event is incapacitating and causes considerable interference with

the subject's usual activities.

10.3 Relationship to Study Treatment

The relationship of each AE to the study drug(s) will be assessed by the Investigator or Sub-Investigator on the basis of his/her clinical judgment and the following definitions:

1= Related:

The AE follows a reasonable temporal sequence from the study product administration, and cannot be reasonably explained by the subject's clinical state or other factors (e.g., disease under study, concurrent diseases, or concomitant medications).

The AE follows a reasonable temporal sequence from the investigational product administration, and represents a known reaction to the drug under study or other drugs in its class, or is predicted by the known pharmacological properties of the drug.

The AE resolves with discontinuation of the investigational product and/or recurs with rechallenge, if applicable.

2 = Not Related:

The AE does not follow a reasonable temporal sequence from investigational product administration, or can be reasonably explained by the subject's clinical state or other factors (e.g., disease under study, concurrent diseases, and concomitant medications).

3= Not Assessable/ Not Classifiable:

The AE cannot be judged because of insufficient or contradictory information. The AE cannot be supplemented or verified.

10.4 Procedures

10.4.1 Collection and Recording of AEs

Collection of all AEs (serious AEs and non-serious AEs) will commence from the time the subject signs the informed consent to participate in the study until the post-treatment follow-up visit. Throughout the in-house treatment period, the Investigator will assess whether any subjective AEs have occurred. In order to avoid bias in eliciting AEs, a non-specific question, such as "How have you been feeling since your last visit?" may be asked. Subjects may report AEs occurring at any other time during the study.

All subjects experiencing AEs, whether considered associated with the use of the study medication or not, must be monitored and given appropriate medical treatment at the discretion and judgement of the Investigator until the symptoms subside and any clinically relevant changes in laboratory values have returned to baseline or until there is a satisfactory explanation for the changes observed. All AEs will be documented in the AE page of the CRF, whether or not the Investigator concludes that the event is related to the drug treatment. The event term, start and stop dates, severity, action taken with study drug and outcome, will be documented, along with the Investigator's opinion of the causal relationship between the event and the study drug.

10.4.2 Collection and Reporting of SAEs

When an SAE occurs, it should be reported according to the following procedure:

An SAE form must be completed immediately or within 24 hours of first onset or notification of the event. The information should be completed as fully as possible but contain, at a minimum a short description of the event and the reason why the event is categorized as serious, subject identification number, Investigator's name, name of the study medication and a causality assessment.

In the interest of subject safety, and in order to fulfill regulatory requirements, all SAEs (regardless of their relationship to study drug) should be reported to the Sponsor or a designated qualified vendor within 24 hours of the Study Center's first knowledge of the event.

The collection of SAEs will begin after the subject signs the informed consent form and stop at the end of the subject's follow-up period. An Initial Serious Adverse Event Form should be completed, and a copy should be faxed to the Sponsor or designated qualified vendor.

All serious and unexpected adverse event reporting will adhere to 21 CFR 312.32 for IND drugs and 21 CFR 314.80 for marketed drugs (15-day alerts). The Institutional

Review Board(IRB) and all Investigators will be notified of the alert reports per FDA regulations.

10.5 Anticipated Adverse Events

Normal precautions taken for a human study, including the provision of emergency equipment, will be taken during this study. Qualified and well-trained physicians and medical staff will instruct the subjects.

Possible anticipated, adverse effects from the study procedure are:

Risks related to repeated blood draws

Subjects will participate in several blood draws throughout the course of the study which have the potential to cause a venous line-vasovagal response, bruising, tenderness, and rarely infection.

10.6 Follow-up of AEs and SAEs

All AEs should be followed up and subjects will be rendered appropriate medical care and treatment at the discretion of the Investigator until resolution or until the Investigator and Sponsor concludes that "further follow-up is not necessary". If the AE has not resolved by the post-treatment follow-up visit, the stop date will be recorded as "ongoing."

All SAEs should be followed up until resolution or permanent outcome of the event or until the Investigator and Sponsor judge that further follow-up is not necessary.

If information is not available at the time of the first report and becomes available later, the Investigator should complete a follow-up SAE form at the earliest possible or provide other written documentation and fax it immediately within 24 hours of receipt of information to the Sponsor or designee. Copies of any relevant data from the hospital notes (e.g., ECGs, laboratory tests, discharge summary, postmortem results) should be sent accordingly.

All other non-serious AEs must be followed until the outcome of the event is "recovering" (for chronic conditions), or "recovered", or until the end of the post-treatment follow-up stated in the protocol, whichever comes first, and until all queries related to these AE's have been resolved.

10.6.1 Safety Reporting to IRBs or IECs, and Regulatory Authorities

The Sponsor or designated qualified vendor will be responsible for reporting all suspected unexpected serious adverse reactions (SUSARs) and any other applicable SAEs to regulatory authorities, Investigators, and IRBs or IECs, as applicable, in accordance with national regulations in the countries where the study is conducted.

Relative to the first awareness of the event by/or further provision to the Sponsor or Sponsor's designee, SUSARs will be submitted within 7 days for fatal and life-

threatening events and 15 days for other SUSARs, unless otherwise required by national regulations.

The Sponsor or designated qualified vendor will also prepare an expedited report for other safety issues where these might materially alter the current benefit-risk assessment of an investigational product or that would be sufficient to consider changes in the investigational product administration or in the overall conduct of the study. The investigational site will forward a copy of all expedited reports to his or her IRB or IEC in accordance with national regulations.

Reporting responsibilities of Investigator under 21 CFR 312.64(b) and Sponsor under 21 CFR 312.32(c)(1)(i) for serious and unexpected suspected adverse reactions will be followed.

11.0 DATA HANDLING AND MANAGEMENT

Clinical Data Management (CDM), including CRF data, is the responsibility of ProSciento. With permission of the Sponsor, CDM may be delegated under an agreement of transfer of responsibilities to a qualified vendor of ProSciento.

11.1 Data Management

The full details of procedures for data handling will be documented in the Data Management Plan (DMP).

AEs and medical history will be coded using the current version of the Medical Dictionary for Regulatory Activities (MedDRA). Concomitant medications will be coded using the World Health Organization (WHO) WHODrug Global.

Unique numbers will identify the subject and the biological material obtained from the subject. Appropriate measures such as encryption or deletion will be enforced to protect the identity of human subjects in all presentations and publications as required by local/regional/national requirements.

Data from screening failures will not be entered into the database.

Laboratory data from the central laboratory will be electronically transferred to ProSciento for database reconciliation purposes. The electronic laboratory data will be considered source data. In cases where sensitive non-PK laboratory data is transferred via non-secure electronic networks, data will be encrypted during transfer.

The laboratory will provide one copy of the laboratory reports to the CRU staff. The staff will receive all laboratory data electronically or based on FAX reports directly from the laboratory. An Investigator must review, evaluate, sign and date the laboratory print-outs upon receipt. The signed print-out of the laboratory reports are source data.

All other results, including PK, PD data, and laboratory tests will be transferred electronically to the responsible Data Management Unit.

11.2 CRFs (Electronic)

11.2.1 Clinical Data Management Workflow

Electronic CRFs will be developed by the CDM department, in collaboration with the clinical study team at ProSciento and statistician. CDM will document the process workflow in the DMP. After data entry, monitor(s) will source data verify (SDV) the eCRFs against the source documents. Queries may be issued to clarify the data entered. The PI will electronically sign the eCRFs after all data have been entered, all queries have been resolved and all external data has been reconciled with the eCRF data. If corrections and/or resolution of queries are required after PI approvals, those eCRFs affected by changes will be re-signed by the PI. The database may be locked after the PI approvals are completed.

After database lock, CDM study design documentation and locked eCRFs (PDF) will be created and will be provided to the Sponsor, if requested.

11.2.2 Data Entry of eCRFs

Data required for analyses and subject safety assessments will be entered from source documentation into eCRFs. Instructions for data entry will be provided in the eCRF Completion Guidelines, developed by the CDM department. All staff involved with entering data into the eCRFs will be trained prior to gaining access to the study database.

11.2.3 Corrections to eCRFs

Queries may be generated by the eCRF system during data entry, and queries may be generated by CDM staff, monitors, and other data reviewers during the course of the study. Only specific CRU personnel will be authorized to make corrections to the eCRFs; CDM will train personnel prior to granting access in the eCRF system. Corrections will be made directly in the eCRF – by modifying existing data, adding new data, or deleting data, as appropriate. All data corrections will be logged in the electronic audit trail.

11.2.4 PI Approval of eCRF Data

The Investigator or Investigator's authorized staff must ensure that all information derived from source documentation is consistent with the source information and accurately reflected in the eCRFs. By electronically signing the eCRFs, the Investigator confirms that the information is complete and correct.

11.3 Retention of Documents

At the completion of the study, all records created by and under the supervision of the Investigator should be maintained in accordance with the requirements of the regulatory authority guideline and the GCP Guideline. These will be available for inspection at any time by the Sponsor or the FDA.

Clinical study documents are archived upon completion of the study and maintained for at least 15 years from the study closure or longer in accordance with local regulation and applicable regulatory authority guidelines, and the study sponsor will be notified prior to destruction of study records.

Current FDA guidelines require records to be retained for a period of 2 years following the date a marketing application is approved for the drug, for the indication for which it is being investigated. If no application is filed or if the application for the investigated indication is not approved, documents will be kept until 2 years after the investigation is discontinued and the FDA is notified. It is the sponsor's responsibility to inform ProSciento as to when essential documents are no longer needed to be retained.

12.0 STATISTICAL METHODS

12.1 Statistical and Analytical Plans

The Sponsor will be responsible for the statistical analysis and the statistical analysis plan (SAP). Statistical services may be delegated under an agreement of transfer of responsibilities to qualified vendors of the Sponsor.

An SAP will be prepared that will provide further details regarding the definition of analysis variables and analysis methodology to address all study objectives. It will also provide any changes or additions to the analyses that are not apparent in the protocol. Procedures for accounting for missing, unused, or spurious data will be discussed in detail in the SAP

12.2 Study Endpoints

The study endpoints or derived parameters used to assess whether the study objectives have been met. The endpoints for this study are shown in Table 12-1. Additional endpoints may be added to the SAP as needed to address the needs of the study.

Table 12-1 Study Endpoints

Primary Endpoints (Safety Endpoints)	Primary Endpoints (Safety Endpoints)	Primary Endpoints	Exploratory Endpoints			
To assess the safety of HM15211	To assess the local tolerability of HM15211	To assess the PK profiles of HM15211	To assess the PD properties of HM15211 compared to placebo			
·Clinical findings on physical examination	·Injection site reaction	•Total AUC, including AUC(0-inf)	·Body weight			
Clinical laboratory abnormalities (including serum amylase, lipase, coagulation, TSH, calcitonin)		·Incremental AUC	·Lipid metabolism (Total cholesterol, LDL, HDL, VLDL, Triglycerides, FFA)			
•Vital signs (BP, respiratory rate, temperature, and HR) measurements		·Cmax	•Glucose metabolism (FPG, Insulin, C- peptide)			
•12-lead ECG parameters (the primary ECG endpoint will be QTcF)		·Tmax	·Incretin secretion (GCG, Leptin, GLP-1, GIP)			
•24-hour ABPM (Mean day- and night time systolic/diastolic BP)		•t _{1/2}	•Inflammatory marker (CRP)			

Primary Endpoints (Safety Endpoints)	Primary Endpoints (Safety Endpoints)	Primary Endpoints	Exploratory Endpoints
•24-hour Holter ECG (HR, HRV (e.g. mean heart rate, difference between day and night HR, mean NN intervals, SDNN)		·CL/F	
·Immunogenicity (ADAbs, nAbs, anti- PEG)		•Vz/F	
·Adverse events		·kel	

12.2.1 Analysis Sets

12.2.1.1 Safety Set

The Safety analysis set will include all subjects who received study medication (HM 15211 or Placebo). The Safety analysis set will be used for demographic, baseline characteristics and safety summaries.

12.2.1.2 Pharmacokinetic (PK) Analysis Set

The PK analysis set will include all subjects who received HM 15211 with all evaluable PK data appropriate for the evaluation of interest (without major protocol deviations or violations that would have an impact on the absorption, distribution, metabolism, or excretion of HM 15211). PK analysis set will be used for analysis of PK endpoints.

12.2.1.3 Pharmacodynamics (PD) Analysis Set

The PD analysis set will include all subjects who received HM 15211 or placebo with all evaluable PD data appropriate for the evaluation of interest (without major protocol deviations or violations that would have an impact on the PD of HM 15211). PD analysis set will be used for analysis of PD endpoints.

12.2.2 Analysis of Demographics and Other Baseline Characteristics

Demographic and baseline characteristics will be summarized for all subjects overall and by cohort and treatment. Summary statistics (e.g., number of subjects, mean, median, standard deviation, and range) will be generated for continuous variables (e.g., age and weight) and the number and percentage of subjects within each category will be presented for categorical variables (eg, gender, ethnicity, and race).

12.2.3 Analysis of the Pharmacokinetic Endpoints

The planned analyses will be described in more detail in the statistical analysis plan (SAP).

The pharmacokinetic endpoints will be derived from the individual serum HM15211 profiles. Serum concentrations of HM15211 will be determined. Non-compartmental analysis (NCA) will be performed for PK parameters such as C_{max} , T_{max} , AUC, $t_{1/2}$, k_{el} , CL/F and V_z /F, will be estimated for each subject. These will be summarized with descriptive statistics by dose and presented graphically if possible. The following descriptive statistics will be presented: n, geometric mean, geometric SD, geometric coefficient of variation (CV), arithmetic mean, arithmetic SD, median, minimum, and maximum. Dose proportionality may be assessed as appropriate. Log-transformation may be applied to these PK endpoints if needed to ensure data normality.

Population PK analysis will be conducted to develop a model for subsequent PK/PD analyses.

12.2.4 Analysis of the Pharmacodynamic Endpoints

Exploratory PD parameters including FPG, insulin, C-peptide, GCG, leptin, GLP-1, GIP as well as CRP, lipid profile, FFA and body weight will be summarized and analyzed.

All PD parameters will be summarized using appropriate descriptive statistics (eg, n, mean or geometric mean, CV, min, median, max) by treatment and collection day as specified in the SAP. The placebo group will be pooled across cohorts in the summary tables.

12.2.5 Safety Analysis and Endpoints

Safety and tolerability of the study drugs will be assessed by collection and review of adverse events, tolerability, laboratory parameters, physical examination, vital signs, and ECG parameters throughout the duration of the study. Immunogenicity of HM15211 will be assessed by the development of ADAbs, nAbs and anti-PEG.

Safety analysis will involve examination of the descriptive statistics and individual subject listings for any effects of study treatment on clinical tolerability and safety.

The 24-hour blood pressure (day and night time systolic/diastolic BP) collected from ABPM, and 24-hour Holter ECG (HR, HRV [eg, difference between day and night HR, NN intervals, SDNN]) will be summarized descriptively.

AEs will be summarized using the safety analysis set. Placebo patients will be pooled across cohorts in the safety analysis.

All AEs will be coded using MedDRA. Data will be summarized using preferred term and primary system organ class.

Adverse event summaries will include the overall incidence (by system organ class and preferred term), events by maximum intensity, event by relationship to study treatment,

events leading to discontinuation of study drug, and serious adverse events. Physical exam, vital signs, blood pressure assessed by ABPM, heart rate assessed by Holter ECG, 12-lead ECG data, and laboratory parameters (hematology, chemistry, and urinalysis) will be summarized descriptively by treatment.

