Subjects will check in to the clinic in the morning on Day -2 for a 9-day In-house Period. They will receive standardized meals throughout their inpatient stay. Subjects will be connected to an ABPM system, and overnight measurements will be taken to familiarize the subjects with the device. ABPM measurements will continue throughout Day 4. Only 24-hour monitoring data from Day -1 will be used for the baseline monitoring evaluation.

In the morning of Day -1, subjects will get connected to a Holter ECG for 24-hour measurements and will continue these until the morning of Day 4. Only 24-hour monitoring data from Day -1 will be used for the baseline monitoring evaluation.

Subjects will be randomized to a single SC injection of HM15211 or placebo.

On Day 1, the active study drug or placebo, will be administered in the morning at approximately 08:00 hours (t=0), SC into the abdominal wall by qualified study staff. Measurements of vital signs, PK and laboratory parameter will be performed for safety evaluation.

ABPM and Holter ECG monitoring will be continued until the morning of Day 4 for the post-dose evaluation. 24-hour monitoring evaluations will be performed together with available PK data, in order to determine the best time period for 24-h monitoring period around PK_{peak}.

Subjects will continue to stay in-house for safety evaluations and PK. They will be released from the clinical research unit (CRU) in the morning of Day 7 and will return for two outpatient visits on Day 10 and 17.

Outpatient Visits:

Subjects will return to the CRU on Days $10 (\pm 1)$ and $17 (\pm 1)$ for two outpatient visits. Blood samples for PK analysis will be collected, additional safety assessments as stated in Table 16-1 will occur.

Follow-up Visit:

A follow-up visit will take place on Day 30 (\pm 2).

	Time points for study procedures and sample collections for PK measurements will be specified in detail in Table 16-1 of the protocol.		
	Safety assessments will occur throughout the duration of the study.		
Treatment	Sample Treatment Schedule:		
	Cohorts	Number of Subjects	Treatment Period
	Cohort 1	N=6	HM15211 - 0.01 mg/kg
		N=2	Placebo
	Cohort 2	N=6	$HM15211 \le 0.02 \text{ mg/kg}$
	Conort 2	N=2	Placebo
	Cohort 3	N=6	$HM15211 \le 0.04 \text{ mg/kg}$
	Condition	N=2	Placebo
	Cohort 4	N=6	$HM15211 \le 0.08 \text{ mg/kg}$
	Conort 4	N=2	Placebo
	Cohort 5	N=6	$HM15211 \le 0.16 \text{ mg/kg}$
	Condition	N=2	Placebo

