4.5 Dose Escalation Algorithm

The proposed dose escalation algorithm for HM15211 may include the following steps:

Table 4-2 Sample Allocation and Dose Escalation

Cohorts	Number of Subjects	Treatment Period	
Cohort 1	N=6	HM15211- 0.01 mg/kg	
	N=2	Placebo	
Cohort 2	N=6	$HM15211 \le 0.02 \text{ mg/kg}$	
	N=2	Placebo	
Cohort 3	N=6	$HM15211 \le 0.04 \text{ mg/kg}$	
	N=2	Placebo	
Cohort 4	N=6	$HM15211 \le 0.08 \text{ mg/kg}$	
	N=2	Placebo	
Cohort 5	N=6	$HM15211 \le 0.16 \text{ mg/kg}$	
Conort	N=2	Placebo	

Each subject will be randomized to HM15211 or placebo according to the table above. The dose will be 0.01 mg/kg, based on the body weight measured prior to dosing. For dose calculation and rounding, please refer to the Operational Manual/Pharmacy Manual.

After at least 6 subjects ($n \ge 4$ subjects on active drug HM15211) in each cohort have completed at least Day 10, safety and available PK data will be reviewed and a dose decision/ dose escalation decision for the subsequent cohort will be made by the Sponsor and the Investigator. Doses between cohorts will not exceed a 2-fold increase relative to the specified doses stated in the Table 4-3 above. Following the dose escalation decision, the procedures for the subsequent cohorts will be identical to those described above.

Adjustments to the procedures/cohorts may occur after the review of available safety and PK data:

- Adjustments to the number of study cohorts may occur: Additional cohorts may
 be enrolled and proceed at a higher or a lower dose. If deemed appropriate by the
 investigator and sponsor, there may be more than one cohort investigated at the
 same dose level.
- Adjustments to the 24-hr BP and HR monitoring: After the evaluation of the first cohort, tests may be rescheduled, or measurement periods may be focused on specific days to capture the 24-h measurement around the PK_{peak}.
- Adjustments to the visit schedule: If PK data suggest, additional sampling times and/or outpatient visits may be added to the study schedule.

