8.0 STUDY MATERIALS

8.1 Investigational Products (IPs)

8.1.1 HM15211

A sterile solution of HM15211 contained in 0.52 mL pre-filled syringes will be provided. The concentration of HM15211 is 10 mg/mL as protein. HM15211 is manufactured by Hanmi Pharmaceuticals, Seoul, South Korea.

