8.1.2 Placebo

Placebo is a sterile, matching solution (all components except drug substance) and free of visible particles. Placebo solution will be supplied in 0.52 mL pre-filled syringes by Hanmi Pharmaceuticals, Seoul, South Korea. Storage: 2 °C to 8 °C.

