8.4 Dose Regimen

The IPs, HM15211 or placebo will be administered after an \geq 10 h overnight fast, by qualified staff while subjects are in the CRU. The products will be administered by SC injection into a lifted skin fold of the abdominal wall. The injection needle should be placed at a 45 to 90° degree angle and kept in the skin fold for 5-10 seconds. Aim is to dose at approximately the same clock time (eg, at approximately 08:00 h) for all subjects. The actual clock time of dosing is defined as t=0. The actual time of each dosing will be recorded in the source documents and on the eCRFs.

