8.6 Randomization and Blinding

To maintain the double-blind of the study, except for the unblinded persons involved in the preparation of the IPs (these persons are not involved in any other study activities), everyone involved in the trial will be blinded until after completion of the study and the final data review. Subjects will be randomized to IP or placebo in a ratio of 3:1 (6 subjects to IP, 2 subjects to placebo) prior to dosing.

Subjects will be randomized to treatment based on a randomization list that will be developed by a statistician. Individual treatment codes, indicating the treatment randomization for each randomized subject, will be available to the Investigator(s) or pharmacy staff at the CRU.

Subjects will be assigned to the lowest randomization number available. Subjects who withdraw prior to dosing on Day 1 may be replaced. If the replacement subject drops from the study, a second replacement subject may be enrolled. Subjects will be replaced at the end of the study following discussion between the Investigator and Sponsor.

The code for a subject may be broken in a medical emergency, if knowing the identity of the treatment allocation would influence the treatment decision of the subject or if demanded by the subject. Whenever a code is broken, the person breaking the code must record the time, date, and reason as well as his/her initials in the source documents. During un-blinding procedure in case of medical emergency, it should be ensured that no study personnel is unblinded to other subjects.

If the CRU need to break the code, the sponsor should, if possible, be contacted prior to breaking the blinding. In all cases, the Trial Monitor must be notified within 24 hours after an emergency un-blinding without revealing the treatment.

All codes (whether broken or not) must be kept throughout the trial period. Accountability of all broken or unbroken codes (hard copy or electronic) will be performed at or after trial closure and will be collected by the Monitor. A copy may be maintained in the Trial Master File (TMF).

The randomization code will include 4-digit subject numbers, 1001-1008 for the first cohort, 2001-2008 for the second cohort and follow the same numbering rationale for cohorts 3 through 5.

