9.1.19 Tolerability Assessments

After injection of the study drug, the injection site will be marked with a pen. Assessment of study drug injection site will be performed pre-dose, at 4 and 12-hour post-dose on Day 1 and then daily from Day 2 to Day 7 (a window of ± 15 minutes is allowed).

The local reaction from the injection site, the insertion site, and the adhesive will be evaluated quantitatively using a Draize scale or similar scale. If an injection site reaction like pain on palpation, itching, erythema, edema, induration is observed, it must be recorded as an AE and then will be evaluated using the following scale:

Erythema will be evaluated as follows:

- 0 No erythema
- 1 Very slight erythema (barely perceptible)
- 2 Well-defined erythema
- 3 Moderate to severe erythema
- 4 Severe erythema (beet redness) to slight eschar formations (injuries in depth)

Edema will be evaluated as follows:

- 0 − No edema
- 1 Very slight edema (barely perceptible)
- 2 Slight edema (edges of area well defined by definite raising)
- 3 Moderate edema (raised approximately 1 mm)

• 4 – Severe edema (raised more than 1 mm and extending beyond the area of exposure)

For the irritation assessment, all irritation events will be documented as AEs. The diameter of the affected area will be measured with a paper measuring tape in centimeter (cm) and the condition of the injection site will be recorded. Digital photography will be used to document all positive injection site reactions. In case of clinically significant injection site reactions, subjects may undergo a dermatological consultation and/or cutaneous biopsies for further histological examination of the injection site reaction. Biopsies will be performed using a 4-mm punch biopsy centered on the injection site. The biopsy area will be anesthetized with lidocaine prior to the biopsy. Wound closure will be performed with Steristrips. If stitches are necessary to close the punch area, they will be removed approximately 2 weeks later. The time between injection and biopsy will be recorded. Microscopic and histological examination of the punch biopsies will be performed at a qualified lab.

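### Does the 0.52 mL syringe size conflict with a single injection in the top cohorts and spoil pooled placebo as the comparator for injection-site reactions?

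*Protocol*

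**What the plan says.** On supply, section 8.1.1 of the protocol says: "A sterile solution of HM15211 contained in 0.52 mL pre-filled syringes will be provided. The concentration of HM15211 is 10 mg/mL as protein". Section 8.1.2 says: "Placebo solution will be supplied in 0.52 mL pre-filled syringes". Sections 2.0 and 4.5 set 0.01 mg/kg for Cohort 1 and ceilings of 0.02, 0.04, 0.08 and 0.16 mg/kg for Cohorts 2 to 5. Section 4.5 bases the dose on body weight measured before dosing and adds: "For dose calculation and rounding, please refer to the Operational Manual/Pharmacy Manual".

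On administration, section 2.0 states: "Subjects will be randomized to a single SC injection of HM15211 or placebo", and section 6.2 repeats it. Section 8.4 says: "The products will be administered by SC injection into a lifted skin fold of the abdominal wall". Section 9.1.19 begins: "After injection of the study drug, the injection site will be marked with a pen", and refers to the site in the singular.

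On preparation, syringes arrive open label (8.2), the sponsor supplies preparation instructions (8.3), and section 8.6 describes the blind with the words "To maintain the double-blind of the study, except for the unblinded persons involved in the preparation of the IPs".

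On analysis, Table 12-1 lists injection-site reaction among the primary endpoints. Section 12.2.5 plans descriptive statistics and individual subject listings, and states: "Placebo patients will be pooled across cohorts in the safety analysis".

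**The concern.** Two things catch the eye.

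First, if the syringe is taken as the unit of dosing, the upper ceilings cannot be given with one syringe to almost anyone with a BMI of 30 or more. The protocol nevertheless speaks of one injection and one site, and does not say how a dose above one syringe is delivered.

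Second, local reactions can come from the act of injecting as well as from the drug. If volume or number of punctures rises with dose, and placebo is matched to active within cohort, the pooled placebo column averages over low and high volumes. The top cohort would then be compared with subjects who on average received less fluid or fewer punctures, and reactions could look dose-related with no drug effect. The placebo volume is not stated at all.

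**Working it through.** The protocol states no content per syringe, injected volume or syringe count, so there is no figure of its own to reproduce.

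**Inputs.** Syringe volume 0.52 mL and concentration 10 mg/mL (8.1.1); ceilings (4.5); BMI 30 to 40 (7.1); 6 active and 2 placebo subjects per cohort (6.1). Height is an assumption: 1.50 to 1.90 m.

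**Content of one syringe.** 0.52 × 10 = 5.2 mg.

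**Weight covered by one syringe** (5.2 / dose per kg):
- 0.04 mg/kg: 130 kg
- 0.08 mg/kg: 65 kg
- 0.16 mg/kg: 32.5 kg

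At BMI 30, 65 kg corresponds to a height of √(65/30) = 1.47 m.

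**Assumed weight range.** 30 × 1.50² = 67.5 kg to 40 × 1.90² = 144.4 kg.

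| Ceiling | Dose | Volume | Syringes |
|---|---|---|---|
| Cohort 4, 0.08 mg/kg | 5.4–11.6 mg | 0.54–1.16 mL | 2–3 |
| Cohort 5, 0.16 mg/kg | 10.8–23.1 mg | 1.08–2.31 mL | 3–5 |

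**Is the syringe the dosing unit?** A 100 kg subject in Cohort 1 needs 1 mg, or 0.1 mL, which is 0.1/0.52 = 19% of a syringe. Part-syringe volumes are therefore needed from the first cohort. The syringe works as a supply container from which a weight-based volume is prepared.

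**Volume imbalance.** At 100 kg the five ceilings give 0.1, 0.2, 0.4, 0.8 and 1.6 mL. If placebo is volume-matched within cohort, the pooled mean is (0.1 + 0.2 + 0.4 + 0.8 + 1.6)/5 = 0.62 mL. That is below active Cohort 5 (1.6 mL) and above active Cohort 1 (0.1 mL).

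**Worst-case illustration.** Assume 100 kg, ceiling doses, matched placebo, one puncture per syringe, independent risk p per puncture and no drug effect. The reaction risk is 1 − (1 − p)^k with k = 1, 1, 1, 2, 4.

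| p | Cohort 5 | Pooled placebo | Gap (points) |
|---|---|---|---|
| 0.05 | 0.186 | 0.087 | 10 |
| 0.10 | 0.344 | 0.167 | 18 |
| 0.20 | 0.590 | 0.310 | 28 |

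With one puncture per subject (k = 1 throughout), the gap is 0 at every p.

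**What a split placebo display would give.** Grouped by k, the ten placebo subjects fall into groups of 6, 2 and 2. Exact 95% upper limits with no events, 1 − 0.025^(1/n), are 46% for 0/6 and 84% for 0/2. A coarser split (Cohorts 1–3 against 4–5) leaves 6 and 4, with 60% for 0/4. At p = 0.10 the placebo risk in Cohorts 4–5 is (0.190 + 0.344)/2 = 0.267. The Cohort 5 gap falls from 17.7 to 7.7 points, but Cohort 4 moves from +2.3 to −7.7.

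**The case for a change.** The strongest case for a change runs as follows. The volume gradient exists whether or not syringes are combined, because concentration is fixed. Section 12.2.5 pools without exception, so the rule is set in the protocol itself. Injection-site reaction is the endpoint for which pooling is hardest to defend, since the procedure can cause the event. Staying below the ceilings does not remove the issue: at 100 kg, any dose above 5.2/100 = 0.052 mg/kg exceeds one syringe. Volume and sites that nobody writes down at dosing may be lost.

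Part of this stands. The arithmetic is right, pooled placebo cannot match every dose group on volume, and the protocol states neither the placebo volume nor how a dose above 5.2 mg is given.

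The rest is weaker. The passages on one injection and one site contain no volume limit, so 0.5 to 2.3 mL at one site does not contradict them; calling that volume unsuitable would need a source outside the protocol. The sized harm depends on several punctures, which the protocol's wording does not describe. For volume alone, the protocol gives no relation to reactions from which to compute an effect.

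Active volume follows, apart from rounding, from assigned dose, Day 1 weight (9.1.5) and concentration. Dispensing is documented (8.3), and a dosing case report form exists, although section 8.5 mentions it only under overdose. Reactions are measured and photographed (9.1.19). Placebo volume is less certain, but within-cohort matching is the natural reading of a double-blind design.

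**Conclusion.** The concern does not call for a change. One syringe holds 5.2 mg, and above 65 kg a dose at either of the top two ceilings exceeds it. This shows missing detail on preparation, which the protocol assigns to the pharmacy manual and the sponsor's instructions. It does not show a contradiction. How such a dose is given is for those documents, and no view on it is taken here.

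Pooling is a fair trade-off. Two placebo subjects per cohort cannot support a comparison by volume, and no hypothesis test (6.3) or escalation stopping rule (6.4.1) uses the pooled column. A reader who sees reactions concentrated in the top cohorts can find the placebo subjects of those cohorts in the listings, because subject numbers encode the cohort (8.6). A supportive table would be optional and would change no result.

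This rests on contents being combined into one injection, or at least on the text not excluding it. If the manual instead prescribes several punctures, a gap of the illustrated size could arise under those assumptions. It would still be a matter of interpreting a descriptive table, to be read with the listings.
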